Total treatment with trial medication will be up to 40 weeks. Total participation in the trial will last up to 52 weeks, including the Screening Period and the EOS Visit.

Reference therapy, dosage, and mode of administration:

Reference product: Placebo (vehicle) in a sterile solution for injection.

Dosage: Placebo QD (titrated in the same manner as active treatment)

Mode of administration: SC injection

Criteria for evaluation:

Primary Endpoint:

- The proportion of patients by genotype who demonstrate a significant clinically meaningful response (defined below) to setmelanotide at the end of Stage 1:
 - For all patients: achieving a $\geq 5\%$ reduction in BMI from Baseline

Secondary Endpoints:

- Mean change and percent change in BMI from Baseline to end of Stage 1 in all patients and patients ≥ 18 years old, per gene
- Mean change and percent change in body weight from Baseline to end of Stage 1 in patients ≥ 18 years old, per gene
- Mean change in BMI Z-score from Baseline to end of Stage 1 in patients < 18 years old, per gene
- Mean percent change in the weekly average of the daily maximal hunger score from Baseline to end of Stage 1 in patients ≥ 12 years old, per gene
- The proportion of patients ≥ 12 years old, per gene, who achieve a ≥ 2 -point reduction (improvement) from Baseline to end of Stage 1 in the weekly average of the daily maximal hunger score.

[REDACTED]

[REDACTED]

Statistical methods:

The primary efficacy endpoint is the proportion of patients by genotype who demonstrate a significant clinically meaningful response (defined below) to setmelanotide at the end of Stage 1:

- For all patients: $\geq 5\%$ reduction in BMI from Baseline

The trial is a 2-stage design: Stage 1 is open-label treatment, and Stage 2 is randomized, double-blind, placebo-controlled.

The 95% exact confidence interval will be provided for the primary efficacy endpoint. The analyses of the efficacy endpoints in Stage 1 will be performed based on the safety analysis set, and the analyses of the efficacy endpoints in Stage 2 will be performed based on the full analysis set (FAS).

AEs/SAEs will be summarized with frequencies and percentages. A by-patient AE data listing including onset and resolution dates, verbatim term, preferred term, treatment, severity, relationship to treatment, action taken, and outcome will be provided.

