In general, unless otherwise specified, events or measurements happen before the randomization date are in Stage 1 and happen on or after the randomization date are in Stage 2. For patients who are not randomized, all events or measurements are in Stage 1. All events happening after visit 14 will not be considered as in Stage 2 for patients who enrolled into bridging visit unless otherwise specified.

D. Definition of Baseline

Baseline Definition

Baseline will be defined as the last non-missing measurement taken prior to the start of stage 1 open-label treatment administration. In the case where the last non-missing measurement and the reference start date coincide and time of measurement is not available, that measurement will be considered Baseline unless the assessment was scheduled to be post-study drug administration in the SOA. Change from baseline is defined as the post-baseline value minus the baseline value, unless specified otherwise. Percent change from baseline = $(\text{Change from Baseline}/\text{Baseline}) \times 100$.

Study Day

Study Day will be calculated from the reference start date within stage and will be used to show start/stop day of assessments and events. Reference start date is defined as the day of first dose (Day 1) in stage1.

Study Day will be computed as follows:

(Confidential)

- Study Day = (date of event - date of first dose in stage 1) + 1 if the date of the event is on or after the date of first dose.
- Study Day = (date of event - date of first dose in stage 1) if the date of the event is prior to the date of first dose.

E. Missing Data

Unless stated otherwise, missing data will not be replaced with imputed values. When relevant, sections below will address how missing data will be handled for the particular analyses.

Analysis Window

All measurements recorded at unscheduled or early termination visits will be mapped according to the windowed visits by actual study day. These records then will be used for analysis if the scheduled ones are missing. If more than one visit occurs within a single visit window, then the analysis will take the one closest to and before the target day. All scheduled assessments will be analyzed according to the protocol defined visits, regardless of the study day

Stage	Study Visit	Study Week	Study Day	Study Day Window
1	Enrollment Visit	1	1	1
1	Virtual Visit 2	2	14	Post-dose - 21
1	Virtual Visit 3	4	28	22 - 35
1	Virtual Visit 4	6	42	36 - 49
1	Visit 5	8	56	50 - 70

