1	Virtual Visit 6	12	84	71 - 98
1/2	In-Person Clinic Visit 7	16/End of Stage 1	112	Patients enrolling in Stage 2: 99 to first dose of Stage 2 Patients not enrolling in Stage 2: 99 - 117
2	Virtual Visit 8	18	126	Post-dose - 133
2	Virtual Visit 9	20	140	134 - 154
2	In-Person Clinic Visit 10	24	168	155 - 182
2	Virtual Visit 11	28	196	183 - 210
2	In-Person Clinic Visit 12	32	224	211 - 238
2	Virtual Visit 13	36	252	239 - 266
2	End of Treatment Visit 14	40	280	266 - 283

Primary Efficacy Endpoint Missing Data Imputation

For patients who do not have BMI value at the end of Stage 1 (Week 16), the unscheduled or early termination weight measurement mapped into Week 16 per visit window will be used for the primary analysis. If weights are measured in triplicate within a same date, the average of the triplicates will be calculated before the BMI calculation. The latest height value will be used together to derive the missing Week 16 BMI.

For patients who still do not have BMI value after above imputation at Week 16, they are treated as non-responder for the primary.

Missing or Partial Adverse Event and Medication Start or Stop Date:

For partial start dates:

- If the year is unknown, no imputation will occur.
- If the year is known and the month and day is unknown, then:
 - If the year matches the year of the first dose date, then impute the month and the day the same as first dose date.
 - If the year is not the same year of the first dose, then month and day will be imputed as 01 January.
- If the month and year is known and the day is unknown, then:
 - If the month and year match the month and year of the first dose date, then impute the day the same as first dose date.
 - If year and month is not the same as the first dose date, then the day will be imputed as "01".

For partial end-dates:

- If the year is missing, no imputation will be performed, and the AE/CM will be assumed as ongoing.
- If the year is present and both month and day are missing and the year is not the same as the last study date, then the month and day will be imputed as the last day of the year, 31 December.
- If the year is present and both month and day are missing and the year is the same as the last study date, then the month and day will be imputed as the last study date.
- If the year and month are present and only the day is missing, and the year and month is not the same as the last study day then the day will be imputed as the last day of the month.

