All patients who are screened (including screen failed).

- **Safety Analysis Set**

All patients who received at least one dose of trial medication.

- **Safety Analysis Set Enrolled in Stage 2**

All patients from Safety Analysis Set who enrolled in stage 2 and received at least one dose of trial medication in stage 2.

- **Full Analysis Set (FAS)**

All patients randomized in Stage 2 who received at least one dose of trial medication (placebo or setmelanotide) after randomization in Stage 2 and have baseline weight data. Analyses performed on the FAS will be based on patients as randomized.

- **Supplemental Analysis Set (SAS)**

All patients who are eligible after the re-confirmatory genetic diagnosis.

M. Special Distribution Schedule

Hunger Questions and [REDACTED] will be recorded as:

Stage 1

Daily [Scenario 1] during the Screening Period, [Scenario 2] for 7 consecutive dates after the enrollment visit, [Scenario 3] for 7 consecutive days starting at Study Days 28, 56, and 84, and [Scenario 4] up to 14 consecutive days starting at Study Day 98. These questionnaires should be completed prior to the morning meal (after an 8-hour fast) and prior to dosing in the morning. During the Screening Period, the patient must complete these questionnaires at least 4 of the 7 days prior to V1 (enrollment visit). If a patient completes V7 (Week 16), and is not continuing into Stage 2 of the trial, the patient will stop completing these questionnaires after completing V7 (and return the electronic diary, if applicable).

Stage 2

[Scenario 2] for 7 consecutive days starting at Study Days 140, 168, 196, 224, and 252, and [Scenario 4] up to 14 consecutive days starting at Study Day 266 (Week 38). These

questionnaires should be completed prior to the morning meal (after an 8-hour fast) and prior to dosing in the morning. All patients will stop completing these questionnaires after Visit 14 (Study Day 280), regardless of whether they have completed the full 14 days of data entry (and return the e-diary, if applicable) or at their Early Termination Visit (if applicable).

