For continuous outcome measure analyses, a weekly average score will be calculated as an arithmetic mean. The baseline score for Stage 1 will still be arithmetic mean of the available score values within 7 days before or on the first dosing (Day 1). For visits in [Scenario 2], [Scenario 3] and [Scenario 4], arithmetic mean of up to 7 measurements that are closest to and before the scheduled visit date will be calculated. For example, measurements taken between Day 1 (V1) to Day 14 (V2) will be labeled as Day 14 (V2) measurement on the table display.

N. Data Display Characteristics

Data displays produced for this study will include three types—summary tables, data listings, and figures. Unless stated otherwise, data listings will be produced for all recorded data. Summary tables will be produced as specified in following sections. Additional data listings will be produced for outcome measures that involve extensive procedures to derive the analyzed outcomes. Figures will be produced when specified in sections to follow.

Listings in general will be presented by gene cohort, stage, then treatment (active and placebo) unless otherwise specified.

Data listings will simply list the data recorded on the CRF or derived for each patient. When expedient, additional levels of ordering hierarchy may reflect subsets of assessments within patient. Data listings will not display patient initials.

Tables in general will be presented by stage unless otherwise specified. In which stage 1 will be presented by overall, each gene in SEMA 3 gene cohort, and gene cohort, stage 2 will be present by overall, each gene in SEMA 3 gene cohort, gene cohort, and treatment (active and placebo).

Tables may have either of two general layouts. When the greatest interest is in direct comparison of one treatment group with the other at particular times, different columns of a summary table will display the statistics for the different treatment groups. The placebo group statistics will be displayed to the left of the treatment group statistics. When the evolution of statistics over time is of greater concern than comparison at particular moments, a group of rows may be designated for the placebo group; the table columns would be designated for different summary statistics of interest. A subsequent group of rows would then be used for the treatment group. In this layout, a group of rows that represent a treatment group would generally be ordered chronologically.

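### SAP V.M collects hunger scores forward from eight mid-stage visits but averages backward from each visit, so these blocks appear at a later visit or go unused, and Week 20 has no post-randomization score

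*SAP*

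**What the plan says.** SAP V.M (Special Distribution Schedule) fixes when the hunger questions are answered. After a 7-day block following enrollment, Stage 1 collects scores "for 7 consecutive days starting at Study Days 28, 56, and 84", then for up to 14 days from Day 98. Stage 2 collects them "for 7 consecutive days starting at Study Days 140, 168, 196, 224, and 252", then for up to 14 days from Day 266. All eight mid-stage start days are scheduled visit days in Protocol Tables 1 and 2.

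For visits after baseline, the weekly value is the "arithmetic mean of up to 7 measurements that are closest to and before the scheduled visit date will be calculated". The one worked example is that "measurements taken between Day 1 (V1) to Day 14 (V2) will be labeled as Day 14 (V2) measurement". The baseline sentence just before it accepts scores before or on Day 1; the rule for later visits says only before.

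Three other places bear on this:
- SAP V.C (Study Stage): "measurements happen before the randomization date are in Stage 1 and happen on or after the randomization date are in Stage 2".
- SAP V.E (Analysis Window) gives each visit a day range and keeps scheduled assessments at their protocol visit. V.M does not refer to it.
- The Protocol Synopsis lists two secondary hunger endpoints in patients aged 12 and over. One is the "Mean percent change in the weekly average of the daily maximal hunger score from Baseline to end of Stage 1"; the other is the proportion improving by at least 2 points over the same interval.

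**The concern.** A diary that starts on the visit day cannot supply the 7 scores before that visit. The rule must then take an older block or find nothing. The hunger time course would be displaced in the tables although the data exist at the right time.

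Stage 2 is the most exposed. Randomization is on Day 112 and the next diary starts on Day 140. If Days 140-146 are shown as Week 24, the first randomized-treatment scores appear four weeks late, and a return of hunger on placebo looks later than it was. Week 20 would be empty or would show open-label scores under a Stage 2 label.

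The Week 16 endpoints raise a second question. The rule has no look-back limit and no minimum count, so a patient with a short final diary could have scores from the Week 12 diary averaged into the end-of-Stage-1 value.

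**Working it through.** **Inputs.** Diary days from SAP V.M: 2-8 (taking the post-enrollment block to start on Day 2), 28-34, 56-62, 84-90, 98-111, 140-146, 168-174, 196-202, 224-230, 252-258 and 266-279. Visit days come from Protocol Tables 1 and 2, windows from SAP V.E, and randomization on Day 112 from Protocol 7.2.2.

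**Rule.** For a visit on Day v, take the up to 7 latest diary days d with d < v. The age of a score is v - d. Visits are on their scheduled day and diaries are complete.

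**The SAP's own example.** For v = 14 the rule selects Days 2-8 and shows them at Day 14, as V.M says. These days lie inside the Week 2 window (post-dose to Day 21).

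**The other diary visits.**

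| Visit (day) | Days selected | Age in days | V.E window | Block starting at this visit |
|---|---|---|---|---|
| Week 4 (28) | 2-8 | 20-26 | 22-35 | 28-34 |
| Week 8 (56) | 28-34 | 22-28 | 50-70 | 56-62 |
| Week 12 (84) | 56-62 | 22-28 | 71-98 | 84-90 |
| Week 20 (140) | 105-111 | 29-35 | 134-154 | 140-146 |
| Week 24 (168) | 140-146 | 22-28 | 155-182 | 168-174 |
| Week 28 (196) | 168-174 | 22-28 | 183-210 | 196-202 |
| Week 32 (224) | 196-202 | 22-28 | 211-238 | 224-230 |
| Week 36 (252) | 224-230 | 22-28 | 239-266 | 252-258 |

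The rule selects 8 × 7 = 56 scores for these visits, and 0 of 56 lie in the labelled visit's window. Each block in the last column lies wholly inside it. Six blocks surface at the next diary visit. Days 84-90 and 252-258 are not used, because Week 16 takes Days 105-111 and Week 40 takes Days 273-279 (1-7 days old, as intended). If Weeks 6 and 18, which have no diary block, are tabulated, they take Days 28-34 and 105-111.

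**Other readings.**
- *V.C applied.* Week 20 is empty, because Days 105-111 precede Day 112. The count becomes 0 of 49.
- *Look-back stopped at the previous visit, as the example suggests.* Weeks 4, 8 and 20 are empty. Days 28-34 appear only at Week 6. Weeks 12, 24, 28, 32 and 36 are unchanged, so 0 of 5 × 7 = 35.
- *Before read as on or before.* Week 20 gains Day 140 only, 1 of 7 scores. In every block 6 of 7 scores still miss their own visit.
- *Actual visit date used, Week 20 visit 3 days late (Day 143).* Days 140-142 count, 3 of 7; with on or before as well, 4 of 7. A visit 3 days early gives 0.

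**Short final diary.** With k < 7 scores in Days 98-111, the unlimited rule takes 7 - k from Days 84-90 (if that block is complete), aged between 112 - 90 = 22 and 112 - 84 = 28 days. For k = 3 this is 4 of 7 (57%); for k = 0 it is all 7. Stopping at the previous visit does not prevent it, since Day 84 is the visit before Day 112. Week 40 behaves the same way with Days 252-258, since Day 252 is the visit before Day 280.

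**The case against.** The strongest reply is that the affected tables cannot be seen. The Stage 2 hunger endpoints, the hunger footnotes and the SAP's hunger analysis text are redacted, and the visible hunger endpoints stop at Week 16, where the rule works with a complete diary. This stands as a limit on certainty: a visit-specific rule may exist, and a Week 20 table is not confirmed. V.M is nevertheless the visible derivation, it speaks of table labels, and its own parts do not fit together.

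The Week 16 top-up is not the most natural reading. V.M sorts visits by scenario, Week 16 has its own block, and the V.E window for that visit reads "Patients enrolling in Stage 2: 99 to first dose of Stage 2", which excludes Days 84-90. These points suggest what was meant, but V.M neither states a block limit nor cites V.E. The 57% describes what the text permits in one case; it is not a forecast.

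The count of 0 in 56 depends on unlimited look-back. That is correct, but the alternatives give 0 of 49 or 0 of 35 and do not move the scores into place. The V.E sentence on scheduled assessments points the other way from V.M, so two programmers could build different tables from this SAP.

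Table 1 also marks hunger questions at the Day 14 and Day 42 visits, with the footnote redacted. A single extra score on those days would enter the Week 4 or Week 8 mean but would lie outside those windows too (22-35 and 50-70).

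Finally, the displays are descriptive, raw scores are listed, and both arms shift alike, so the error is in the time label. All of this holds and bounds the importance. The blinded review in V.O is a weak safeguard, because it follows collection of all data, whereas V.J produces the Stage 1 analyses earlier.

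**Conclusion.** The concern holds. Followed exactly, V.M shows none of the eight mid-stage blocks at its own visit: six are displaced to the next diary visit at 22-28 days old, and two are unused when end-of-stage diaries are complete. Week 20 has no randomized-treatment score on scheduled dates; looser readings give at most 4 of 7 in the cases examined. The Week 16 secondary endpoints are affected only in patients with fewer than 7 scores in Days 98-111.

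This rests on scheduled visit days, a strict reading of before, and no overriding rule in the redacted text; confidence is therefore medium. The primary endpoint is untouched and no hypothesis test depends on these values. It should be fixed because the stated rule mislabels data that the trial does collect. No labelling rule can recover Days 112-139, when no diary is scheduled.

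**What to change.** Replace the averaging rule in SAP V.M with text to this effect:

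> For each 7-day diary block that starts on a scheduled visit day v (28, 56, 84, 140, 168, 196, 224, 252), the weekly average is the mean of the available scores from Day v to Day v+6, displayed at that visit. For Weeks 16 and 40 it is the mean of the last up to 7 scores before the visit, drawn only from the block starting on Day 98 or Day 266; if that block has no score, the value is missing. No score from before randomization is displayed at a Stage 2 visit. Weeks 6 and 18 have no diary block and receive no value.

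Keep the Week 2 example, stated as a rule, since Days 2-8 fall inside that visit's window. With complete diaries, Weeks 4, 8, 12, 20, 24, 28, 32 and 36 then each have 7 of 7 scores from their own block, and Week 20 has 7 scores on randomized treatment. Neither the plan nor this text sets a minimum number of scores for a weekly average.

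The cost is two or three sentences and one derivation change, with no new data collection. A few more Week 16 or Week 40 hunger values may be missing. The change should be made before the Stage 1 analyses described in V.J, and any redacted hunger text should be checked against it.
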